## 1. **BACKGROUND**

### 1.1 **PATHOPHYSIOLOGY**

Polypoidal choroidal vasculopathy (PCV) is a type of choroidal neovascularization (CNV) that has occult characteristics on fluorescein angiography but demonstrates saccular dilations and polypoidal interconnecting vascular channels on indocyanine green angiography. PCV results in serosanguinous pigment epithelial detachments (PED) and neurosensory retinal detachments secondary to leakage and bleeding from the choroidal vascular lesions. PCV is a distinct clinical syndrome and the aneurysmal dilatations may be visible clinically as reddish-orange. PCV was originally recognized as a “uveal bleeding syndrome” often presenting with multiple recurrent hemorrhagic PED’s in middle-aged, pigmented females. With time and recognition, a broader concept of PCV has occurred, including a broad range of ages, races including a propensity for Asians as well as African Americans, and both sexes (Yannuzzi 1997). While debated, the pathogenesis of the vascular abnormality in PCV has been proposed to be a likely variant of CNV (Uyama 1999), although others propose PCV as inner choroidal vessel abnormalities that are distinct from CNV (Yuzawa 2005). Within the expanding spectrum of PCV, there is some overlap in elderly patients initially classified as age-related macular degeneration (AMD). PCV may be differentiated from AMD in that PCV is more commonly observed in the peripapillary region, without associated drusen, and in non-white patients (Yannuzzi 1999). While the natural course of PCV is somewhat more favorable than AMD-associated CNV, active polypoidal lesions often cause subfoveal hemorrhagic PED’s, subretinal fluid/exudates and fibrosis resulting in visual loss.

The stimuli that prod are unknown. However, there is evidence suggesting that angiogenic factors, such as vascular endothelial growth factor (VEGF), play a role in the pathogenesis of AMD-related CNV and in all forms of ocular neovascularization (see section 1.3). Systemic hypertension is associated with PCV.

## **1.2 TREATMENT OF PCV**

Observation for asymptomatic, non-exudative PCV is recommended. The efficacy of any treatment modality for active, exudative PCV has not been established as large controlled trials have not been performed. Anecdotal evidence in case series indicates that PCV may respond to thermal laser (often ICG-guided) photocoagulation (Uyama 1999, Yannuzzi 1990, Nishijima 2004) or photodynamic therapy (PDT) with Visudyne (Spaide 2002, Chan 2004, Silva 2005, Nazimul 2005). Other therapies for CNV such as periocular steroids (Okubo 2005), submacular surgery (Matsuoka 2004) and transpupillary thermotherapy (TTT) (Vedantham 2005) have been published as single case reports indicating possible benefit for PCV. Other CNV therapies such as intravitreal steroids, radiotherapy, and translocation surgery have not been the focus of published reports in PCV patients.

## **1.3 RANIBIZUMAB AND PCV**

There is well-established evidence suggesting that angiogenic factors, such as vascular endothelial growth factor (VEGF), play a major role in the pathogenesis of AMD-related CNV and in all forms of ocular neovascularization. Anti-VEGF therapy with aptamers (Gragoudas 2004) and with antibodies (Brown 2006, Rosenfeld 2006) has been demonstrated to be beneficial therapy for neovascular AMD. Surgically-excised PCV lesions demonstrate strong VEGF expression thus indicating a likely role for VEGF in PCV proliferation and exudation (Matsuoka 2004, Terasaki 2002). In addition, a significant increase of aqueous humor VEGF was found in eyes with exudative PCV (Tong 2006). This rationale has led to investigation of intravitreal anti-VEGF therapy for exudative PCV.

Gomi and coworkers (Gomi 2008) assessed the short-term efficacy of intravitreal bevacizumab (Avastin, Genentech Inc., San Francisco, CA) for 11 Asian eyes with PCV. One or two bevacizumab injections resulted in decreased OCT thickness at 1 month. This anatomical effect was lost at 3 months. Lesion size improved in one eye but residual or enlarged lesions were observed in the other 10 eyes. There were no

significant short-term effects on visual acuity. The authors proposed that a single bevacizumab injection is insufficient and that repeated bevacizumab injections or alternative anti-VEGF agents with greater retinal penetration or VEGF affinity may be required (Gomi 2008). Song and coworkers (Song 2009) similarly evaluated a single intravitreal bevacizumab injection in 19 Asian eyes and observed improvement at 3 months in both OCT retinal thickness and visual acuity. Fluorescein angiographic leakage was reduced at 3 months and partial polyp regression occurred in more than 50% of eyes. ICG angiography demonstrated no changes in the choroidal branching vessels suggesting that bevacizumab may not penetrate deeply enough to effect the more mature choroidal vascular abnormalities (Song 2009). Lai and coworkers (Lai 2008) treated 15 Asian PCV eyes with three monthly bevacizumab injections with or without PDT. At 3 months, visual acuity and OCT thickness improved. Persistent polyps were present in all eyes but subsequent PDT did lead to lesion regression in some eyes. The authors concluded that bevacizumab monotherapy has limited effect on lesion regression and proposed that combination bevacizumab with PDT may be optimal (Lai 2008). Lee and coworkers (Lee 2008) treated 8 Asian PCV eyes with bevacizumab alone and 4 Asian PCV eyes with combination bevacizumab and PDT. With mean followup of 17 weeks visual acuity, OCT thickness, and angiographic leakage improved. Partial or complete lesion regression occurred in most eyes. The authors proposed that bevacizumab monotherapy may be adequate therapy for less advanced lesions (Lee 2008).

There are just two published reports evaluating ranibizumab (Lucentis, Genentech Inc., SanFrancisco, CA) for PCV. Reche-Frutos and coworkers (Reche-Frutos 2008) noted that 3 monthly ranibizumab injections improved visual acuity and OCT thickness at 3 months follow-up in a Hispanic population. Polyp regression was observed in 9 of 13 eyes. The authors proposed that in comparison to bevacizumab, ranibizumab's deeper penetration may be responsible for the favorable polyp regression rate (Reche-Frutos 2008). Kokame and coworkers (Kokame 2009) treated 12 Asian PCV eyes with continuous monthly ranibizumab. Six month results indicated improved subretinal fluid, macular edema, and hemorrhage in the majority of eyes. One third of

eyes demonstrated decrease lesion size but branching choroidal vessels were unchanged. A press release from QLT Inc. (QLT Inc. 2009) reported results from the EVEREST prospective, randomized study evaluating ranibizumab monotherapy versus PDT monotherapy versus ranibizumab/PDT combination therapy for 61 eyes with Asian PCV. At 6 months the ranibizumab monotherapy, PDT monotherapy, and ranibizumab/PDT combination groups gained 9.2, 7.5, and 10.9 letters, respectively. Complete polyp regression occurred in 29%, 71% and 78% of eyes in the ranibizumab monotherapy, PDT monotherapy, and ranibizumab/PDT combination groups, respectively (QLT Inc. 2009).

The above data evaluating anti-VEGF therapy for PCV is limited by a relatively small number of treated eyes, short follow-up and absence of comparison groups. However, given the encouraging results of the above limited data along with the known favorable results of anti-VEGF therapy for neovascular AMD, as well as the overlap between exudative AMD and PCV, further evaluation of anti-VEGF therapy for PCV is needed. In addition, evaluation of anti-VEGF therapy for PCV has primarily occurred in an Asian population and little or no data exist for African-American and Caucasian populations. In fact, African-Americans are hardly represented in neovascular AMD anti-VEGF trials. Ethnic differences in PCV may well affect treatment responses due to genetic makeup, variances in the natural history of disease, and living environments.

We previously enrolled 20 non-Asian PCV eyes and evaluated intravitreal ranibizumab (0.3mg and 0.5 mg) for exudative PCV. Subjects included 16 African-Americans (12 female, 4 male) and 3 male Caucasians. The mean age was 63.6 years and the mean follow-up for the present ongoing study is 18 months. Mean baseline BCVA was 20/127 (range, 20/16-20/500) and CPT was 298  $\mu$ m. Mean BCVA increased from baseline by 1.2 and 1.5 ETDRS lines at 12 and 24 months, respectively. Four of 14 eyes and 3 of 12 eyes gained  $\geq 3$  lines BCVA at 12 and 24 months, respectively. Mean CPT decreased from baseline by 53  $\mu$ m and 67  $\mu$ m at 12 and 24 months, respectively. Eyes received a mean of 7.2 injections during a mean follow-up of 19 months. Visually

significant ocular adverse events included cataract progression (n=3), mild vitreous hemorrhage (n=2), and macular hole (n=1). No systemic drug-related adverse events were observed.

Intravitreal ranibizumab was well tolerated in non-Asian patients with PCV; the majority of eyes experienced improvements in BCVA and CPT following ranibizumab treatment.

Clinical data of intravitreal anti-VEGF therapy indicate a need for multiple injections to maintain a beneficial effect for AMD, as well as for diabetic macular edema (DME). Similarly, for PCV, data outlined above indicates a need for multiple anti-VEGF injections and an absence of lesion regression with anti-VEGF monotherapy. Thus, dose-escalation of ranibizumab has been investigated using 1.0 and 2.0 mg doses for AMD and DME to assess if higher doses have greater efficacy and/or require less injections. Early studies for AMD and DME indicate higher doses are likely safe and may improve visual and anatomic outcomes. The HARBOR study (FVF4579g) is a phase III randomized trial (Genentech Inc., San Francisco, CA) comparing 2.0 mg to 0.5mg ranibizumab for neovascular AMD.

Evaluation of ranibizumab at higher doses is especially needed for PCV as limited data indicates lesions are recalcitrant to standard dose monotherapy. In addition, African Americans are underrepresented in AMD trials. We propose to evaluate high dose (2.0 mg) ranibizumab in previously treated and treatment naïve PCV eyes.

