The Sailor study (FVF3689g) evaluated the safety of intravitreal ranibizumab in a large population of subjects with CNV secondary to AMD. Subjects in Cohort 1 (N=2378) were randomized (1:1) to receive ranibizumab at a dose level of 0.3 mg or 0.5 mg; subjects were masked to these dose levels. Treatment was administered monthly for three initial doses (Day 0, Month 1, and Month 2), with scheduled follow-up visits on Months 3,6,9, and 12. Retreatment after the first three injections was performed as needed, on the basis of predefined criteria with injections no more frequently than every 30 days.

Cohort 2 (N=1992) consisted of subjects enrolled after the majority of Cohort 1 subjects had been enrolled, with enrollment continuing until ranibizumab was approved or denied by the FDA for US marketing, and if approved, until commercially available or 30 September 2006, whichever was earlier. Subjects in Cohort 2 received open-label ranibizumab at the 0.5 mg dose level, with an initial injection on Day 0 followed by retreatment at the physician's discretion, no more frequently than every 30 days. Subjects were monitored for safety for a total of 12 months; safety information, including both serious and nonserious adverse events, was collected at every clinic visit, with two formal safety visits scheduled at Months 6 and 12.

The study consisted of a 30-day screening period and a 1-year treatment period. Treatment duration was approximately 197 days for both dose groups in Cohort 1 and 144 days for subjects in Cohort 2. The mean follow-up time differed between Cohort 1 and Cohort 2, 337 days versus 254 days, respectively.

Ranibizumab was well tolerated, and the incidence of ocular SAEs and AEs was low and unrelated to dose. The rates of individual key ocular SAEs in Cohort 1 were < 1% and were similar across dose groups. Endophthalmitis or presumed endophthalmitis developed in 0.2% subjects in the 0.3-mg group and 0.4% subjects in the 0.5-mg group. The incidence of ocular inflammation, including iritis, uveitis, vitritis, and iridocyclitis was 1.9% in the 0.3-mg group and 1.5% in the 0.5-mg group. Overall cataract rates were 5.4% (0.3 mg) and 6.0% (0.5 mg) and were similar when broken down by nuclear, subcapsular, and cortical subtypes. The rates of individual key ocular SAEs in Cohort 2 were <1%.

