### **Secondary Outcome Measures**

- Month 3, 6, 9, 12 best corrected visual acuity at 4 meters – rates for gain of 5,10 and 15 or more letters
- Month 3, 6, 9, 12 best corrected visual acuity at 4 meters- rates for loss of 15 or more letters
- Median and Average best corrected visual acuity at 4 meters- gain/loss (letters) at 3,6,9,12 months.
- Mean change from baseline in central foveal thickness over time up to 12 months as assessed on OCT
- Mean change from baseline in macular volume overtime up to 12 months.
- Proportion of patients with no evidence of fluid from CNV as assessed by OCT at 12 months.
- Mean change from baseline in the total area of CNV fluorescein angiographic leakage overtime up to 12 months.
- Mean change from baseline in total area of ICG CNV lesion size (including polyps and deep choroidal vessels) overtime up to 12 months.
- Fluorescein and ICG angiograms and fundus photographs will also be graded at each time point compared to baseline as unchanged, resolved, improved, worsened, or cannot determine. For the FA and ICG evaluations, “resolved” will be defined as no leakage and no evidence of polyps or PCV choroidal lesion; “improved” will be defined as decreased leakage and/or decreased size, number, or hyperfluorescence of polyps and/or PCV choroidal lesion; and “worsened” will be defined as increased leakage and/or increased size, number or hyperfluorescence of polyps and/or PCV choroidal lesion. For fundus photography evaluations, “resolved” will be defined as no evidence of PED, subretinal fluid, hemorrhage, or hard exudate; improved will be defined as a decrease in PED,

subretinal fluid, hemorrhage, or hard exudate; and “worsened” will be defined increase in PED, subretinal fluid, hemorrhage, fibrosis, or hard exudates.

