#### 4.1.2 **Inclusion Criteria**

Subjects will be eligible if the following criteria are met. *Any deviation/waivers granted regarding inclusion/exclusion criteria will be reviewed by the principal investigator and fully documented.*

- Males and Females >18 years of age. *Females of child bearing potential will undergo urine pregnancy testing* and be required to use appropriate methods of birth control.
- ICG and fluorescein angiographic characteristics consistent with active, leaking PCV with subfoveal lesions &/or subfoveal hemorrhage, lipid exudates, PED or fluid diagnosed within the past 6 months or diagnosed as newly active within the past 6 months. Subjects who completed the 24 month follow up in the original FVF3671s protocol may enter the extension study with 2.0 mg without necessarily demonstrating active exudative PCV at enrollment.
- Best-Corrected ETDRS Visual Acuity at 4 meters between 20/20 – 20/800
- Lesion size- no limitations
- Lesion Characteristics- leaking lesions consistent with PCV. No limitations on hemorrhage, fibrosis or atrophy.
- No therapy (includes non foveal laser, PDT, intravitreal steroids, TTT, radiotherapy, or anti-VEGF therapy) or intraocular surgery within the past 30 days for any condition.

- Clear ocular media to allow for photography/angiography.
- Ability to provide written informed consent and comply with study assessments for the full duration of the study

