### 4.8.3 Efficacy Analyses

1. **Primary Endpoint-** See Section 3.3.1

2. **Secondary Endpoints-** See Section 3.3.2

All subjects will be used in analysis of primary and secondary outcome parameters. Rates for the endpoints at the suggested time points will be presented as a % of the patients enrolled. Analysis of Variance will be used to assess for role of variables in for the endpoints. Variables will include # Ranibizumab injections, other therapies, baseline acuity, age, gender, etc.

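### Section 4.8.3 does not separate acuity measured after cataract or other intraocular surgery in a study eye, so in this uncontrolled 20-eye series a lens gain could be read as a drug gain

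*Combined protocol and SAP*

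**What the plan says.** - **Endpoints.** The secondary outcome measures in Section 3.3 include, at Months 3, 6, 9 and 12, "rates for gain of 5,10 and 15 or more letters", the rate of losing 15 or more letters, and the median and average change in letters.
- **Analysis set.** Section 4.8.3 states: "All subjects will be used in analysis of primary and secondary outcome parameters". Rates are percentages of those enrolled. Section 4.8.4 uses available cases without imputation.
- **Surgery.** The only restriction is at entry: Section 4.1.2 rules out "intraocular surgery within the past 30 days for any condition". Surgery in a study eye after entry does not appear in Section 4.4 (concomitant and excluded therapies), among the listed reasons in Section 4.6 (discontinuation), or in Sections 4.8.3 and 4.8.4. Section 3.4 has surgeries reported as safety events.
- **Lens at entry.** Section 4.1.2 asks only for media clear enough for imaging. Section 3.1 lets up to 10 of the 20 eyes come from the earlier cohort after 24 months.
- **How often cataract is seen.** For the earlier cohort, Section 1.3 lists these visually significant events: "significant ocular adverse events included cataract progression (n=3), mild vitreous hemorrhage (n=2), and macular hole (n=1". For the large safety study in neovascular AMD, Section 1.5 gives: "Overall cataract rates were 5.4% (0.3 mg) and 6.0% (0.5 mg".

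**The concern.** Cataract was the most frequent visually significant ocular event listed for the earlier cohort, so surgery in a study eye during the acuity follow-up is foreseeable. Acuity gained by replacing an opaque lens says nothing about the PCV lesion. With a single arm, no comparison removes it.

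The route to a false gain is specific: the lens must already limit acuity at baseline, and the eye must be operated and remeasured by Month 12. The entry criteria leave this open. An eye carried over from the earlier cohort could bring opacity acquired there into its new baseline and then, once operated, count as a gainer on 2.0 mg.

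Acuity is a secondary outcome, but it is the first secondary objective (Section 2.2), and Section 3.2 expects the study to inform potential efficacy. If no rule is written beforehand, the handling of one or two influential eyes will be decided after their results are known.

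**Working it through.** The plan has no sample size calculation and no stated figure on this point to reproduce. The check asks how many eyes could be affected and how far they could move the results.

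**Inputs from the documents**
- Earlier cohort (Section 1.3): "We previously enrolled 20 non-Asian PCV eyes and evaluated intravitreal ranibizumab"; 3 eyes with cataract progression.
- Its follow-up: "Eyes received a mean of 7.2 injections during a mean follow-up of 19 months". The same section also gives a mean of 18 months.
- Its acuity result: "Mean BCVA increased from baseline by 1.2 and 1.5 ETDRS lines at 12 and 24 months, respectively". At 12 months, 4 of 14 eyes had gained 3 lines or more.
- One-year safety study (Section 1.5): cataract in 5.4% and 6.0%.
- Planned size: 20.

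**Step 1: affected eyes in 12 months**
- Crude proportion: 3/20 = 15.0% (exact 95% interval 3.2% to 37.9%), over 18 to 19 months.
- Rescaled under a constant hazard, 1 − (1 − 0.15)^(12/f): f = 18 gives 10.3%; f = 19 gives 9.8%. Times 20: 2.05 and 1.95 eyes.
- At the safety-study rates: 20 × 0.054 = 1.08 and 20 × 0.060 = 1.20 eyes.
- About 1 to 2 eyes are therefore expected. The chance of at least one among 20, 1 − (1 − p)^20, is 67% to 71% at the safety-study rates and 87% to 89% at the rescaled site rate.

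These are eyes with cataract or its progression. The documents give no surgery rate.

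**Step 2: effect on the acuity results**

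Let k be the number of operated eyes and L the letters each gains over *baseline* through surgery. Both are assumptions: k = 0 to 2, L = 0 to 15.
- Shift in a letter-gain rate: at most k/20. This is 0 for k = 0, 5 points for k = 1 and 10 points for k = 2, if each eye crosses the threshold only because of surgery.
- Shift in the mean: k × L/20. This runs from 0 to 2 × 15/20 = 1.5 letters.

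**Step 3: yardstick**
- Section 3.3.1 gives a 30-letter loss and Section 3.4 a 6-line loss, which is consistent with 5 letters per line. The earlier 12-month gain is then 1.2 × 5 = 6 letters, and 1.5/6 = 25% of it.
- The earlier rate of gaining 3 lines or more was 4/14 = 29%. Its denominator is not the planned 20, so it is only a rough yardstick for the 0 to 10 points.

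**The case against.** A reader might infer from the three eyes in Section 1.3 that lens surgery *would* turn up to 3 of the 20 eyes into responders. The documents do not support that reading:

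- They report progression, not surgery. How many eyes would be operated, and whether they would be remeasured by Month 12, is unknown.
- The three cases arose over 18 to 19 months, while acuity endpoints stop at Month 12. About 2 eyes is the fairer figure from that source.
- Change is measured from baseline. Surgery that only reverses progression arising on study restores a loss and adds roughly nothing. The requirement for media clear enough to image makes a large gain over baseline less likely, though it does not rule one out.
- Progression that is not operated lowers acuity, so the net direction is unknown.
- It would also be an inference that the 30-day entry rule shows the plan regards surgery as disturbing the measurements. Section 4.1.2 gives no reason for that rule.

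All of this stands, and it is why the range starts at zero.

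The plan does have some related provisions. Surgeries are reported under Section 3.4, a serious event may lead to discontinuation under Section 4.6, and Section 4.8.3 names other therapies as an ANOVA variable. Operated eyes would therefore probably be identifiable. But elsewhere the plan's examples of such therapies are laser, PDT and steroids, and an ANOVA term does not change the reported rates and means.

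A last objection concerns the remedy. If post-surgery gains were removed from the main result while pre-surgery losses stayed in, the summary would be lopsided. Section 1.5 lists traumatic cataract among injection-related serious events, so eyes could be dropped because of a treatment complication. With enrolled patients as denominator, an excluded eye would also count as a non-gainer. These points argue against making exclusion the main analysis. They do not argue against showing both results.

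**Conclusion.** The gap is real and of modest size. Nothing in the plan separates post-surgery acuity, and by default it enters every acuity summary. Assuming 0 to 2 operated eyes and 0 to 15 letters gained over baseline by each, the effect is 0 to 10 percentage points in a gain rate and 0 to 1.5 letters in a 20-eye mean, which is at most a quarter of the earlier cohort's gain of about 6 letters. The upper end needs two eyes to be operated, recovered and measured by Month 12, with lens opacity already limiting acuity at entry.

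The documents do not show that this will happen, and they do not fix the net direction of bias. The primary safety outcome does not depend on the point. It deserves correction because a possible lens effect cannot otherwise be told from a drug effect in a small single-arm series, and the data needed are already scheduled.

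**What to change.** Add to Section 4.8.3:

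1. The analysis of all available values remains the main result.
2. For every acuity endpoint alike (gain rates, loss rate, mean and median change), a pre-specified sensitivity line excludes study-eye values obtained after cataract or other intraocular surgery. Values before surgery stay in at the visits where they were measured.
3. The denominator of the sensitivity line is the number of eyes contributing at that visit. With g gainers of whom k were operated, the reader then sees g/20 beside (g − k)/(20 − k), if all 20 eyes are measured and the k eyes were operated before that visit.
4. A listing gives each operated study eye, the surgery date, and lens status at baseline and follow-up.

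Lens status can be taken from the slit-lamp examinations in Section 3.1, and surgery dates from the adverse event and concomitant medication review in Appendix A. No visit or procedure is added and patient care does not change.

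The cost is one extra line per acuity table and a short listing. The sensitivity line will probably rest on one or two fewer eyes at later visits, and it should be read as a check on the main result, not a replacement.
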